15. EFFICACY OUTCOMES

15.1. PRIMARY EFFICACY

15.1.1. PRIMARY EFFICACY VARIABLE

The primary efficacy endpoint is the change from baseline RDQ symptom scores for the GERD dimension (heartburn and regurgitation) after a 7-day treatment period of a regimen of two Compound Sodium Alginate Double Action Chewable Tablets taken four times daily compared with a matched placebo. This variable is derived from the data collected on the “Reflux Disease Questionnaire” form in eCRF.

The RDQ is a self-administered questionnaire in which subjects are asked to report the frequency and severity of their upper gastrointestinal symptoms (refer to Appendix 1 and 2 of the Protocol). There are three subscales that evaluate regurgitation, heartburn and dyspepsia. The heartburn and regurgitation subscales can be combined into a GERD dimension. Refer to Appendix 2 for RDQ scoring instructions for deriving the RDQ symptom scores for the GERD dimension.

15.1.2. MISSING DATA METHODS FOR PRIMARY EFFICACY VARIABLE

For those patients that do not return for Visit 3 because of confirmed poor efficacy from the treatment between Day 1 and Day 6, all efficacy data at Visit 3 will be imputed as no change from the day 0 values (BOCF) if Early Termination visit is missing. If there is missing data for a patient in the RDQ questionnaire at an occasion and the missing data is less than or equal to 50% of the item scores within a dimension, the missing items will be imputed using the mean score of the non-missing item scores. If more than 50% of the item scores are missing, no imputation will be performed and the dimension score will be excluded from the analysis.

Document: Reckitt Benckiser GA1210 Statistical Analysis Plan

Author: [REDACTED]

Version Number:

2.0

Version Date:

29Jul2014

Template No: CS_TP_BS016 – Revision 3

Reference: CS_WI_BS005

Effective Date: 01May2012

Page 15 of 23

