11.3.2.2 Clinical Assessments at Visit 3, End of Treatment

Visit 3 will take place preferably on the day following completion of 7-days of study treatment, ie, Day 8, or if necessary up to 1 day before and 2 days after that (Day 7 to Day 10). At this visit, the patient will complete the RDQ questionnaire and answer questions relating to overall satisfaction with the trial therapy (OTE) over the previous seven days. All unused and empty study medication containers will be returned for assessment of compliance with treatment. The following will be completed:

Vital Signs

- Blood pressure (after sitting for 5 minutes; mmHg).
- Heart rate (radial pulse counted for 30 seconds after resting for 5 minutes; beats/minute).

Concomitant Medication

- All concomitant medication usage including any OTC medications and traditional Chinese medicines will be recorded.

Adverse Events

- All adverse events will be recorded.

Physical examination

- A standard physical examination will be conducted.

Laboratory investigations

- Haematology
- Biochemistry

- Details are listed in section 13.4.

Pregnancy testing

- Women of child-bearing potential will undergo urine pregnancy testing.

11.3.2.3 Clinical Assessments at Early Termination (ET) Visit (only if required for patient early terminations)

The patient will be instructed to return to the investigator before the end of treatment if they require further treatment for their GERD symptoms or have unacceptable adverse events. Early termination applies to study Days 1 to 6. If the investigator withdraws the patient from the study for these or any other reasons the patient will complete the study at this early termination visit and the following will be completed.

The patient will complete the RDQ questionnaire and answer questions relating to overall satisfaction with the trial therapy (OTE) over the study treatment period. All unused and empty study medication containers will be returned for assessment of compliance with treatment. The following will be completed:

Vital Signs

- Blood pressure (after sitting for 5 minutes; mmHg).
- Heart rate (radial pulse counted for 30 seconds after resting for 5 minutes; beats/minute).

Concomitant Medication

- All concomitant medication usage including any OTC medications and traditional Chinese medicines will be recorded.

Adverse Events

- All adverse events will be recorded.

Physical examination

- A standard physical examination will be conducted.

Laboratory investigations

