14 STATISTICAL CONSIDERATIONS

The statistical analysis will be undertaken in collaboration with Quintiles.

A detailed Statistical Analysis Plan will be finalised before the code for all patients is broken and prior to analysis of the study being carried out.

Any deviations from the analyses described below will be included in the Statistical Analysis Plan, which will form Appendix 16.1.9 of the clinical study report.

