14.4 Efficacy Analyses

Efficacy data will be recorded from the RDQ questionnaire and the patient overall treatment evaluation (OTE).

All efficacy data will be listed in the appendices of the study report and summarised for the ITT and PP populations by treatment group (n as the number of observations, mean, median, SD, minimum and maximum). Categorical variables will be summarised by treatment group using frequency distributions (showing cell frequencies and percentages).

For those patients that do not return for Visit 3 because of confirmed poor efficacy from the treatment between Day 1 and Day 6, all efficacy data at Visit 3 will be imputed as no change from the day 0 values (BOCF). All other withdrawn patients that do not have the reason of withdrawal confirmed as poor efficacy and do not complete the Visit 3 assessments will be treated as missing. If the number of such patients is high, a sensitivity analysis will be conducted to assess the robustness of this imputation and the effect on results.

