7.3. RETESTS, UNSCHEDULED VISITS AND EARLY TERMINATION DATA

In general, for by-visit summaries, data recorded at the nominal visit will be presented. Unscheduled measurements will not be included in by-visit summaries. In the case of a retest (same visit number assigned), the latest available measurement for that visit will be used for by-visit summaries.

Early termination data will be mapped to the next available visit number, i.e., Visit 3, for by-visit summaries.

Listings will include scheduled, unscheduled, retest and early discontinuation data.

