15.2.2 MISSING DATA METHODS FOR SECONDARY EFFICACY VARIABLES

For those patients that do not return for Visit 3 because of confirmed poor efficacy from the treatment between Day 1 and Day 6, all efficacy data concerning RDQ scores at Visit 3 will be imputed as no change from the day 0 values (BOCF) if Early Termination visit is missing. If there is missing data for a patient in the RDQ questionnaire at an occasion and the missing data is less than 50% of the item scores within a dimension, the missing items will be imputed using the mean score of the non-missing item scores. If more than 50% of the item scores are missing, no imputation will be performed and the dimension score will be excluded from the analysis.

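### The SAP's zero-change rule for treatment failures depends on a missing Early Termination visit, not a missing RDQ score, so a known failure can be in ITT with no value in the models

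*SAP*

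**What the plan says.** Protocol 14.4 sets the rule "For those patients that do not return for Visit 3 because of confirmed poor efficacy from the treatment between Day 1 and Day 6": their Visit 3 efficacy data become zero change, with no mention of an ET visit. It then says that "All other withdrawn patients that do not have the reason of withdrawal confirmed as poor efficacy and do not complete the Visit 3 assessments" are treated as missing.

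SAP 15.1.2 repeats the zero-change rule for the primary endpoint with an added condition: "all efficacy data at Visit 3 will be imputed as no change from the day 0 values (BOCF) if Early Termination visit is missing". SAP 15.2.2 carries the same condition for the secondary RDQ scores: "imputed as no change from the day 0 values (BOCF) if Early Termination visit is missing". Both sections exclude a dimension score when more than half of its items are missing, and neither falls back to zero change in that case.

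Four other provisions bear on this:

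- SAP 6.3 admits to ITT any recruited patient known to have withdrawn for poor efficacy, with or without an RDQ.
- Protocol 11.3.2.3 states "Early termination applies to study Days 1 to 6" and requires the RDQ at that visit.
- The protocol's schedule of assessments labels ET as replacing Visit 3.
- SAP 7.3 says "Early termination data will be mapped to the next available visit number, i.e., Visit 3, for by-visit summaries".

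**The concern.** ITT admits poor-efficacy withdrawals without an RDQ, and the zero-change rule gives them a value. In the SAP that rule is switched off by attendance at ET, whether or not attendance produced a score. A failure who skips ET is scored zero, while one who attends and leaves the form largely blank is dropped. Nothing in the SAP justifies treating the two differently.

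The condition also bears on failures with a usable ET score. The RDQ asks about the past 7 days and dosing starts the day after randomisation, so a form completed on Days 1 to 6 covers some days before treatment. Using that score instead of zero change may be reasonable, but it is an analysis choice. The SAP leaves it to be inferred, because SAP 7.3 speaks only of by-visit summaries.

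At stake are which known failures enter the two confirmatory models, and with what value.

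**Working it through.** **The plan's own figures.** Pilot effect sizes: 0.61/0.9735 = 0.627 and 0.43/1.121 = 0.384, as stated. A two-group t-test at effect size 0.2, two-sided 5% and 90% power needs 526.3, so 527 per arm and 1054 in total, as stated. Power at 527 per arm is 0.900 for effect size 0.2 and above 0.999 for 0.4. None of these figures is in question.

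**The rules side by side, for a confirmed poor-efficacy withdrawal on Days 1 to 6:**

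| Situation | Protocol 14.4, read literally | SAP 15.1.2 and 15.2.2 |
|---|---|---|
| A. No ET visit | zero change | zero change |
| B. ET attended, usable dimension score | zero change | ET score (implied) |
| C. ET attended, dimension score unusable | zero change | no value, though in ITT |

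Case C requires at least 5 of 8 GERD items, or 3 of 4 dyspepsia items, to be missing.

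**Size.** The documents give no count of failures, so what follows is a range under assumptions.

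Inputs from the protocol: 1100/2 = 550 per arm; planned difference d = 0.4 × 0.9735 = 0.3894 points (GERD) and 0.2 × 1.121 = 0.2242 points (dyspepsia).

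Assumed: the failure counts; a mean change in the other placebo patients, m_P, of -0.5 to -1.5; m_A = m_P - d on active.

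*Case C.* Let p_A and p_P be the shares of each arm affected. Scoring zero gives a difference of (1 - p_A)m_A - (1 - p_P)m_P. Dropping gives m_A - m_P. The shift, dropping minus zero-scoring, is p_A·m_A - p_P·m_P.

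- 1% of each arm: shift = 0.01 × (-d) = -0.0039 (GERD) and -0.0022 (dyspepsia). That is 1% of the effect, away from zero.
- 3 active and 8 placebo, GERD: at m_P = -0.5, -(3/550)(0.8894) + (8/550)(0.5) = -0.0049 + 0.0073 = +0.0024. At m_P = -1.5, -(3/550)(1.8894) + (8/550)(1.5) = -0.0103 + 0.0218 = +0.0115. That is 0.6% to 3.0% of 0.3894, toward zero.
- Same counts, dyspepsia: -0.0040 + 0.0073 = +0.0033, and -0.0094 + 0.0218 = +0.0124. That is 1.5% to 5.5% of 0.2242, toward zero.
- Extreme bound: all 1100 - 1054 = 46 planned losses are placebo failures with unusable ET forms. The shift is (46/550) × 0.5 to 1.5 = 0.042 to 0.125.

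*Case B.* If the mean ET change is c in both arms, the shift (SAP minus literal protocol) is (p_A - p_P)c. With 3 and 8 failures and c from -0.5 to +1.0, it runs from +0.005 to -0.009. With 46 failures, all on placebo, it runs from +0.042 to -0.084.

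**Whether a planned analysis already tests this.** The sensitivity analyses in SAP 15.1.4 and 15.2.4 use the PP population. SAP 6.4 excludes patients seen outside Days 7 to 10 unless they withdrew for lack of efficacy. Other-reason ET attenders are therefore removed, but confirmed failures without another major deviation stay in, with the same SAP values. The PP analysis does not test the choice in Case B or fill the gap in Case C.

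**The case against.** The strongest reply is that the documents do not conflict. ET replaces Visit 3 in the schedule and the RDQ is required there. An ET attender can therefore be taken to have completed the Visit 3 assessments, and protocol 14.4 then covers only patients with nothing observed. On that reading the SAP condition is a clarification. This is a fair reading, and a reader should not infer as settled that the two documents build different primary data sets. It is not the only reading: protocol 14.4 addresses the same Day 1 to 6 window as ET and makes no exception for attenders. Case C remains in the SAP on either reading.

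A reader might also infer an undisclosed or data-driven change. The documents do not support that. Protocol 14 says "Any deviations from the analyses described below will be included in the Statistical Analysis Plan", the rule is written openly in two SAP sections, and the data review held before the SAP was finalised was blind.

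On size, three replies stand. The 5% drop-out allowance (about 55 of 1100) is a ceiling on all drop-outs, not a count of affected patients. Patients who never attend ET are scored alike under both documents if they are confirmed failures. A mostly blank form completed in clinic is probably rare.

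It can finally be said that a missing ET visit was meant as a missing ET RDQ. That may be so, but the SAP does not say it.

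**Conclusion.** The point holds as a gap in a stated rule. Under SAP 15.1.2 and 15.2.2, a confirmed failure who attends ET without a usable dimension score belongs to ITT but contributes nothing to the primary or key secondary model. The same condition leaves the use of valid ET scores implied, and it departs from protocol 14.4 if that section is read literally.

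The likely effect is small: about 1% of the treatment effect for each 1% lost equally from both arms, and up to 3.0% (GERD) or 5.5% (dyspepsia) in the 3-versus-8 illustration. These figures rest on assumed failure counts and mean changes. With more failures on placebo, dropping them moves the estimate toward zero. Primary power above 99% makes a changed primary conclusion unlikely. The key secondary has less slack, at 90% power for an effect size of 0.2. The larger shifts need all 46 planned losses to be placebo failures who attended ET, which is a bound and not an expectation.

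**What to change.** 1. In SAP 15.1.2 and 15.2.2, replace the closing condition about the ET visit with: if no valid dimension score is available from Visit 3 or the Early Termination visit. Take valid to mean no more than half of the items missing, as in 15.1.2; 15.2.2 does not say what happens at exactly half.
2. State that valid ET RDQ scores are used as Visit 3 values in the models, not only in by-visit summaries.
3. Repeat the primary and key secondary models under the literal protocol 14.4 rule as a supportive sensitivity analysis: all confirmed poor-efficacy withdrawals who did not return for Visit 3 at zero change, and other withdrawals without Visit 3 missing.

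The cost is two sentences and one extra run of two models. The change form dated 1 September 2014 at the end of the SAP shows that unblinded output had by then been reviewed, so the change would be recorded as made after unblinding, by the same route.

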9.3 Discussion of Study Design

The primary endpoint and some of the secondary endpoints are assessed using information collected in the Reflux Disease Questionnaire (RDQ). The choice of the RDQ is based on this being a validated questionnaire which collects patient assessments of their heartburn, acid regurgitation and dyspepsia. The RDQ is validated in English (Appendix 1) and Chinese Mandarin (Appendix 2). It comprises a 12-item self-administered questionnaire which was designed to assess the frequency and severity of heartburn, acid regurgitation and dyspepsia symptoms. The heartburn and acid regurgitation subscales can be combined into a GERD dimension [9]. Response options are scaled as Likert-type with scores ranging from 0 to 5 for frequency (not present to daily) and severity (not present to severe).

Other secondary endpoints are assessed using the Overall Evaluation of Treatment (OTE). The OTE is a validated scale that rates the overall change in clinical status on a 15-point scale (-7 to -1 = worse; 0 = no change or about the same; and +1 to +7 = better). It then categorises the change with a second question asking how patients perceive the importance of the change on a 7-point scale from: 1 = not important, 2 = slightly important, 3 = somewhat important, 4 = moderately important, 5 = important, 6 = very important, 7 = extremely important [11-13].

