14.1 Sample Size Justification

In a previous pilot study conducted in the UK (GA1203), a least square mean difference (Gaviscon – Placebo) of -0.61 was obtained from the ANCOVA model comparing the change in the GERD dimension score from the RDQ after 1 week. The root mean squared error (RMSE) from the ANCOVA model, which included treatment as a fixed effect and the day 0 RDQ GERD dimension score as a covariate, was 0.9735.

In the same study, a least square mean difference (Gaviscon – Placebo) of -0.43 was obtained from the ANCOVA model comparing the change in the Dyspepsia dimension score from the RDQ after 1 week. The root mean squared error (RMSE) from the ANCOVA model, which included treatment as a fixed effect and the day 0 RDQ Dyspepsia dimension score as a covariate, was 1.121.

For the purposes of sample size estimation using the module for a two-group t-test between equal means in NQuery Advisor 7.0, the least square means difference and RMSE from GA1203 will be used to estimate the effect sizes. The effect sizes using these results would be estimated as 0.627 for the GERD dimension and 0.384 for the Dyspepsia dimension.

In other previous studies, different endpoints to the RDQ were used to demonstrate the efficacy of Gaviscon Original Liquid compared to Placebo Liquid. The percentage of patients that rated a positive improvement in symptoms were reported. In a study conducted in the UK (0900901), 74% of Gaviscon Original patients had a positive improvement of symptoms compared to only 44% of Placebo patients. When a similar study was conducted in China (GA0917), the corresponding results were 77% for Gaviscon Original and 67% for Placebo, thus suggesting an increased Placebo effect in the Chinese population compared to the UK population.

Assuming a reduced effect size of 0.2 for the Dyspepsia dimension, this would require a total of 1054 patients with evaluable dyspepsia data from the RDQ to have 90% power to show a statistical significant difference at the 5% level using a two-group t-test. The actual analysis method to be used would be an ANCOVA model with treatment as a fixed effect, centre as a random effect and the day 0 RDQ Dyspepsia dimension score as a covariate.

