14.4.3 Statistical Methods for Efficacy Analyses

All statistical tests performed will be 2-tailed with significance assessed at the 5% significance level. The null hypothesis at all times will be the equality of the treatments being compared.

Normality assumptions will be evaluated by an examination of the residual plots. Depending on the degree of departure from these assumptions, an alternate nonparametric approach may be used for supportive purposes.

The primary endpoint (change in RDQ GERD dimension score) will be analysed using an analysis of covariance (ANCOVA) model with a fixed effect term for treatment, centre as a random effect and the day 0 RDQ GERD dimension score as a covariate. Treatment group differences will be estimated using the least square means and presented with 95% confidence intervals and p-values to make inferences.

The change in symptom score for each dimension separately will be analysed identically to the primary endpoint although the included covariate will be the relevant dimension day 0 score rather than the GERD dimension score.

To preserve the type 1 error rate of 5% for the key secondary endpoint (change from day 0 in RDQ scores for dyspepsia dimension), a closed testing procedure will be applied. A significant comparison at the 5% level ($p<0.05$) for this key secondary endpoint will only be deemed as confirmatory evidence if the primary endpoint is also significant at the 5% significance level ($p<0.05$). All other secondary endpoints and/or any further sensitivity or alternate analyses for the primary and key secondary endpoint will serve as supportive evidence only and therefore no further adjustment for multiple comparisons will be made.

For the primary and key secondary endpoint, two additional separate exploratory ANOVA models will be conducted identical to those stated above but with one additional interaction term for the treatment by centre interaction (random effect) and treatment by baseline covariate interaction respectively.

The change scores in frequency and intensity for each dimension as well as the two OTE responses will be compared between treatments using a Wilcoxon Rank Sum Test stratified by centre.

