23 APPENDICES

23.1 Appendix 1 English version Reflux Disease Questionnaire

Reflux Disease Questionnaire (RDQ)						
Please answer each question by ticking one box per row.						
1. Thinking about your symptoms over the past 7 days, how often did you have the following?						
	Did not have	1 day	2 days	3-4 days	5-6 days	Daily
a.						
b.						
c.						
d.						
e.						
f.						
2. Thinking about your symptoms over the past 7 days, how would you rate the following?						
	Did not have	Very mild	Mild	Moderate	Moderately severe	Severe
a.						
b.						
c.						
d.						
e.						
f.						

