APPENDIX 2 REFLUX DISEASE QUESTIONNAIRE (RDQ)

Description

The RDQ is a self-administered questionnaire. It has been used to assess treatment induced changes over time and will be validated as a diagnostic tool of gastroesophageal reflux disease for use in primary care.

Scoring

The questionnaire, which contains 12 items, uses a six-graded Likert scale, where 0 represents the most positive option and 5 the most negative one. A raw score is calculated.

A mean value for the items in each dimension should be calculated:

Heartburn: 1a. A burning feeling behind your breastbone

1b. Pain behind your breastbone

2a. A burning feeling behind your breastbone

2b. Pain behind your breastbone

Regurgitation: 1e. An acid taste in your mouth

1f. Unpleasant movement of material upwards from the stomach

2e. An acid taste in your mouth

2f. Unpleasant movement of material upwards from the stomach

GERD dimension: 1a. A burning feeling behind your breastbone

1b. Pain behind your breastbone

2a. A burning feeling behind your breastbone

2b. Pain behind your breastbone

1e. An acid taste in your mouth

1f. Unpleasant movement of material upwards from the stomach

2e. An acid taste in your mouth

2f. Unpleasant movement of material upwards from the stomach

Dyspepsia: 1c. A burning feeling in the centre of the upper stomach

1d. A pain in the centre of the upper stomach

2c. A burning feeling in the centre of the upper stomach

2d. A pain in the centre of the upper stomach

References:

- Shaw M. Diagnostic utility of reflux disease symptoms. *Gut* 2004;53(Suppl IV):iv25-iv27.

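### An RDQ item left blank beside a paired score of 0 is known to be 0, but the SAP fills it with the dimension mean, so the score is too high when another item is above 0

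*SAP*

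**What the plan says.** SAP 15.1.2 (primary, GERD dimension) imputes blank RDQ items when "the missing data is less than or equal to 50% of the item scores within a dimension". In that case "the missing items will be imputed using the mean score of the non-missing item scores". SAP 15.2.2 repeats the rule for the dyspepsia, heartburn and regurgitation scores, with a slightly different limit: "the missing data is less than 50% of the item scores within a dimension". Neither section mentions the pairing of items.

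SAP Appendix 2 defines the scores: "A mean value for the items in each dimension should be calculated". Items 1a to 1f are frequency and 2a to 2f are severity of the same six symptoms, and both items of a pair always fall in the same dimension. The GERD score has eight items (four symptoms) and each of the other three scores has four items (two symptoms).

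Protocol 9.3 describes the response options as "scores ranging from 0 to 5 for frequency (not present to daily) and severity (not present to severe", and Table 2 in Protocol 11.4.1.2 labels 0 as none on both scales. Both questions on the form cover the past 7 days (Protocol Appendices 1 and 2).

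**The concern.** Mean imputation suits an item whose value is unknown. A severity item left blank by a patient who has just scored the frequency of that symptom as 0 is not unknown, and the same holds the other way round. The SAP rule replaces the known 0 with an average that includes symptoms the patient still has. It can produce a record in which a symptom never occurred yet has a severity of 2 or 3.

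For a single score the error is never downward. At Visit 3 it hides part of the improvement of a patient who has lost a symptom. If lost symptoms are commoner on active treatment, the between-arm difference is pulled towards zero for the primary and key secondary endpoints. One blank item is enough, so the problem lies inside the imputation limits of both sections. It is separate from the mismatch between those limits at exactly 50% missing.

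**Working it through.** **The plan's own figures.** For effect size 0.2, two-sided 5% and 90% power (Protocol 14.1), the normal approximation gives 2 × (1.960 + 1.282)² / 0.2² = 525.4, so 526 per arm. The noncentral t gives 527 per arm, 1054 in total, with power 0.9004, which matches the plan. In RDQ points the planning effects are 0.4 × 0.9735 = 0.39 (GERD) and 0.2 × 1.121 = 0.22 (dyspepsia). The point below does not depend on these figures.

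**Error in one score.** Let T be the sum of the observed items, m the number of items in the dimension, and k the number of blanks whose paired item is 0, with no other blanks. Filling with the mean of the observed items gives T/(m − k). Filling with the known zeros gives T/m. The error is T/(m − k) − T/m = Tk / [m(m − k)]. It is 0 when T = 0 and positive otherwise.

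| Dimension | Symptoms gone, one item of the pair blank | Other items | SAP score | With zeros | Error |
|---|---|---|---|---|---|
| GERD (m = 8) | 1 | all 3 | 18/7 = 2.57 | 18/8 = 2.25 | +0.32 |
| GERD | 2 | all 3 | 12/6 = 2.00 | 12/8 = 1.50 | +0.50 |
| GERD | 3 | all 3 | 6/5 = 1.20 | 6/8 = 0.75 | +0.45 |
| GERD | 4 | none left | 0 | 0 | 0 |
| GERD, largest | 2 | all 5 | 20/6 = 3.33 | 20/8 = 2.50 | +0.83 |
| Four-item (m = 4) | 1 | both 3 | 6/3 = 2.00 | 6/4 = 1.50 | +0.50 |
| Four-item, largest | 1 | both 5 | 10/3 = 3.33 | 10/4 = 2.50 | +0.83 |

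**Both occasions.** SAP 15.1.2 applies the rule at any RDQ completion. Inclusion criterion 5 (Protocol 10.1) admits patients with heartburn, regurgitation or both, with or without dyspepsia, so absent symptoms at Day 0 are to be expected. A Day 0 score that is too high makes that patient's improvement look larger, not smaller. Randomisation should balance this between arms.

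**Between-arm effect.** The documents give no blank rate, so two sets of assumptions were simulated. Both compare mean scores or changes without the mixed model.

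1. *Blanks clustered in patients, Visit 3 only.* A fixed share of patients skips the severity row of any absent symptom, and each symptom is absent in 40% (active) against 30% (placebo). There were 200,000 patients per arm.

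| Patients who skip | GERD, zeros → SAP rule | Shrinkage | Dyspepsia, zeros → SAP rule | Shrinkage |
|---|---|---|---|---|
| 5% | −0.295 → −0.292 | 1.0% | −0.295 → −0.294 | 0.3% |
| 10% | −0.299 → −0.294 | 1.7% | −0.296 → −0.292 | 1.4% |
| 20% | −0.297 → −0.285 | 4.0% | −0.303 → −0.297 | 2.0% |

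2. *Blanks scattered over items, Day 0 and Visit 3.* Each symptom is present at Day 0 with probability 0.75 at level 3, and falls to 2 if it persists. It resolves in 45% against 19% (GERD) or 40% against 25% (four-item). There were 400,000 patients per arm. With 20% of zero-scored pairs half blank, the SAP difference is 0.997 (GERD) and 0.998 (four-item) of the difference with zeros. With 50% it is 0.985 and 0.995.

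**Effect on power.** If the true dyspepsia effect is 0.2, the RMSE is unchanged and 2% is lost, the effect becomes 0.196. Then 0.196 × √(527/2) = 3.18, and 3.18 − 1.96 = 1.22, which gives power of about 89% instead of 90%. A 4% loss on GERD gives an effect of 0.384, and power stays above 99%.

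**The case against.** The strongest objection is that the triggering record may hardly occur. The form says "Please answer each question by ticking" one box per row, and each severity row has its own box for not having had the symptom. The Mandarin version has a none column as well. There is no skip pattern, the RDQ is completed at a clinic visit, and Protocol 18.1 has the investigator and the monitor review the eCRF for completeness. All of this stands: it makes blanks less likely, but does not exclude them. The SAP itself foresees missing items.

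It is also fair to say that the paired 0 is not ignored, because it is one of the observed items that are averaged. It is given too little weight, and the arithmetic above already includes it.

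A third objection is that the rule is prespecified, clear and reproducible, and that a pair rule goes beyond Appendix 2. The first part is true. But Appendix 2 asks only for a plain item mean, and a pair rule does not conflict with that.

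A reader might infer three stronger things that the documents do not support:

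- *Every patient who has lost a symptom is scored too high.* This needs a blank item and another item above 0 in the same dimension.
- *The rule always understates improvement.* At Day 0 it does the opposite.
- *The error rivals the effect the trial is sized on.* This sets one patient's score error (up to 0.83) against a difference between group means (0.39 or 0.22). At group level the illustrated loss is at most about 0.01 points.

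**Conclusion.** The point holds as a small, avoidable scoring error. A value that the patient's own paired answer fixes at 0 is replaced by a mean, and the dimension score is too high whenever another item in that dimension is above 0. The error is at most 0.83 points for that patient when such blanks are the only ones, at Day 0 as well as at Visit 3 or early termination.

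The effect on the treatment comparison is about 0 to 4% towards zero. That range rests wholly on assumed blank and resolution rates, since the documents give none. If there is no treatment effect and skipping is equal between the blinded arms, the rule creates no expected difference, so no inflation of type I error is expected. The trial's conclusion is not in question on this ground. The planned sensitivity analyses (SAP 15.1.4 and 15.2.4) change only the population to PP, so they would not reveal the error.

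**What to change.** In SAP 15.1.2 and 15.2.2, insert before the mean-imputation sentence:

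> If one item of a symptom's frequency/severity pair is 0 and the other is missing, the missing item is set to 0 and counted as non-missing. The 50% rule and mean imputation then apply to any items still missing.

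Apply it at Day 0 and at Visit 3 or early termination, to all four dimension scores.

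The change note dated 1 September 2014 at the end of the SAP shows that unblinded output had already been reviewed by then. If the analysis is complete, count the records in which one item of a pair is 0 and the other blank, by arm and occasion. If there are any, rerun the dimension scores with the paired zeros as a labelled supportive analysis beside the prespecified result.

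The cost is one sentence in two sections and a few lines of derivation code, with no new data and no use of treatment codes in the rule. The downside is a small departure from the stated item-imputation rule, which the report should note.
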